2.3. Hypotheses

Primary Hypotheses

1. After 25-31 days of wear, the binocular, high-luminance, high-contrast distance (4 M) logMAR visual acuity of the test lens will be statistically better than 0.00 logMAR. This will be determined using ETDRS LogMAR acuity testing charts.
2. After 25-31 days of wear, the binocular, high-luminance, high-contrast intermediate (64 cm) logMAR visual acuity of the test lens will be statistically better than +0.17 logMAR. This will be determined using Guillon/Poling LogMAR acuity testing charts.
3. After 25-31 days of wear, the binocular, high-luminance, high-contrast near (40 cm) logMAR visual acuity of the test lens will be statistically better than +0.17 logMAR. This will be determined using Guillon/Poling LogMAR acuity testing charts.

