4. STUDY DESIGN AND RATIONALE

4.1. Description of Study Design

The study is a bilateral, single-masked, single-arm, 4-visit dispensing study. Approximately 90 subjects will be enrolled with target completion of at least 80 subjects.

The study begins with an initial visit (Visit 1). If a subject is found to meet all eligibility criteria, they will be dispensed the study lens in a bilateral fashion.

If the subject is dispensed study lenses at the initial visit, then three follow-up visits will occur. The first follow-up visit will occur approximately one week after the initial visit. If necessary, the lens power may be modified at Visit 2, then a new pair of lenses with the final lens power will be dispensed. The second follow-up (Visit 3) will occur approximately 14 days after Visit 2 and the third and final follow-up evaluation (Visit 4) will occur approximately 28 days after Visit 2.

Clinical Study Protocol

Johnson & Johnson Vision Care, Inc.

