5. TEST ARTICLE ALLOCATION AND MASKING

5.1. Test Article Allocation

This is a single-arm study. All subjects will be dispensed the study lens in a bilateral fashion.

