14.4. Level of Statistical Significance

All planned analysis for this study will be conducted with an overall type I error rate of 5%.

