14.5. Primary Analysis

LogMAR Visual Acuity

Binocular, high luminance, high contrast visual performance on logMAR scale will be analyzed using a linear mixed model. Each model will include the experimental design factors: distance (distance/intermediate/near) as fixed effect. Site will be included as random covariate when appropriate. Other baseline characteristics known of importance such as age, gender and/or add power will be included as fixed covariates when appropriate. The covariance between residual errors from the same subject across different distances will be selected based on the finite-sample corrected Akaike's Information Criterion (Keselman et al. 1998).⁸ Covariance structures considered may include: Homogenous compound symmetry (CS) and Unstructured covariance structure (UN). The structure that returns the lowest Akaike Information Criteria Corrected (AICC) will be selected as the structure that best fit the data.

Clinical Study Protocol

Johnson & Johnson Vision Care, Inc.

The Kenward and Roger method will be used for the calculation of the denominator of degrees of freedom.⁹

Comparisons will be carried out using 95% confidence intervals constructed of least-square means (LSM) from the linear mixed models. Statistically superiority will be concluded if the upper limits of the confidence intervals are below the thresholds for corresponding distances.

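### Optional covariates in the single-arm primary model can shorten or shift the intervals that are tested against fixed acuity thresholds, and the plan does not say which mean is being tested

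*Combined protocol and SAP*

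**What the plan says.** Section 5.1 states: "This is a single-arm study. All subjects will be dispensed the study lens in a bilateral fashion". Section 2.3 sets three one-sample hypotheses on binocular, high-luminance, high-contrast acuity after 25 to 31 days of wear. The distance claim is that "logMAR visual acuity of the test lens will be statistically better than 0.00 logMAR". The near claim is that "high-contrast near (40 cm) logMAR visual acuity of the test lens will be statistically better than +0.17 logMAR", and intermediate has the same +0.17 threshold.

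Section 14.5 fits a linear mixed model with distance as a fixed effect and, optionally, site as a random effect. It adds: "Other baseline characteristics known of importance such as age, gender and/or add power will be included as fixed covariates when appropriate". The decision rule is in two sentences: "Comparisons will be carried out using 95% confidence intervals constructed of least-square means (LSM) from the linear mixed models", and "Statistically superiority will be concluded if the upper limits of the confidence intervals are below the thresholds for corresponding distances".

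The plan gives no final covariate list and no rule for when a covariate is appropriate. It does not give the covariate values or weights at which the LSMs are evaluated. Nor does it say whether the target is a population mean or a mean at fixed covariate values.

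**The concern.** In a randomised comparison, a prognostic covariate removes noise from a difference between arms. Here a single mean is set against a constant. Evaluating the LSM at the sample mean of a continuous covariate returns the raw mean, so the estimate becomes no more precise for the population. The model standard error, however, contains residual variance only and treats the sampled ages or adds as fixed. The upper limit falls although the uncertainty about the population mean has not changed.

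A class covariate raises a different issue. Default LSMs usually weight the levels equally, so the tested mean belongs to a 50:50 mix whatever was enrolled. Gender is a class variable. Add power could be one too, since the lens comes as Low or High (section 6.1), or it could enter in dioptres (section 3.2).

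All three superiority conclusions rest on these upper limits.

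**Working it through.** **Inputs.** n = 80, the completion target in section 4.1. The decision rule is that of section 14.5, read as a two-sided 95% interval, so 2.5% one-sided per distance. R2, the share of acuity variance explained by the covariates, is an assumption. Section 14.2 reports no power calculation, so there is no planned figure to reproduce.

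**Continuous covariate, or class covariate at observed margins (complete data).**
- Estimate: the raw mean, with true sampling SD sigma/sqrt(n).
- Model standard error: sigma × sqrt(1-R2)/sqrt(n).
- One-sided error at the threshold: Phi(-1.96 × sqrt(1-R2)).
- Coverage of the population mean: 2 × Phi(1.96 × sqrt(1-R2)) - 1.

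| Assumed R2 | Width ratio sqrt(1-R2) | One-sided error | Coverage |
|---|---|---|---|
| 0 | 1.000 | 2.5% | 95.0% |
| 0.05 | 0.975 | 2.8% | 94.4% |
| 0.1 | 0.949 | 3.1% | 93.7% |
| 0.2 | 0.894 | 4.0% | 92.0% |
| 0.3 | 0.837 | 5.1% | 89.9% |
| 0.4 | 0.775 | 6.4% | 87.1% |

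**Simulation, one endpoint** (n = 80, 20,000 trials). At R2 = 0.1, 0.2 and 0.3, one-sided error was 3.0%, 4.0% and 4.7% with the covariate, and 2.3% to 2.5% without it. The sampling SD of the estimate stayed at 0.110 to 0.112 SD units throughout.

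**Simulation, three distances** (unstructured covariance, assumed within-subject correlation 0.4, 4,000 trials). Error with the covariate was 2.9% to 3.4% at R2 = 0.1 and 4.2% to 4.7% at R2 = 0.3. Without it, error was 1.9% to 2.6%.

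**Site variance.** Covariates measured on subjects do not reduce site variance. As an illustration, assume 5 sites and 5% of variance between sites.
- True variance of the mean: 0.05/5 + 0.95/80 = 0.021875.
- Model variance at R2 = 0.2: 0.01 + 0.011875 × 0.8 = 0.0195. The ratio is 0.891, and Phi(-1.96 × sqrt(0.891)) = 3.2%.
- Model variance at R2 = 0.4: 0.01 + 0.011875 × 0.6 = 0.017125. The ratio is 0.783, and the error is 4.1%.

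These compare with 4.0% and 6.4% when site variance is ignored.

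**Class covariate with equal-weight LSMs.** Assume a 35:65 population split and R2 = 0.1.
- Difference between levels: sqrt(0.1/(0.35 × 0.65)) = 0.663 SD.
- Shift of the LSM: (0.50 - 0.35) × 0.663 = 0.099 SD.
- Standard error: sqrt(0.9) × sqrt(1/80 + 0.15²/(80 × 0.2275)) = 0.111 SD, so the shift is 0.89 standard errors.
- Error if the larger group has the worse acuity: Phi(-1.96 + 0.89) = 14%.
- Error if the larger group has the better acuity: Phi(-1.96 - 0.89) = 0.2%.

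In simulation with a 50:50 split, error stayed at 2.6% and precision truly improved (sampling SD 0.107 against 0.112 at R2 = 0.1). With a 30:70 split at R2 = 0.1, the interval was about 5% wider than the unadjusted one.

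**The case against.** The best reply is that inference conditional on observed covariates is ordinary regression practice, and that section 2.3 speaks of the lens without defining a mean over randomly sampled covariates. For a conditional target the shorter interval is valid. That stands, but the plan does not say that a conditional mean is intended. The hypotheses name no age, gender or add at which the claim is made.

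It is also true that covariates are optional, that nothing narrows if they do not predict acuity, and that R2 of 0.05 to 0.1 costs little. The study is described as a pilot. These points limit the size of the effect, and they are accepted.

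Four stronger readings are tempting, and the documents do not support them:
- **Covariates always narrow the interval.** They may not be used at all. With equal-weight class LSMs the interval can widen, or precision can genuinely improve.
- **The 5% overall error rate of section 14.4 is breached.** On the two-sided reading, error per distance passes 5% only at R2 = 1 - (1.645/1.96)² = about 0.30. If all three hypotheses must succeed, the overall error cannot exceed that of a single test. If any one may succeed, multiplicity is a separate question that exists without covariates.
- **Equal weighting moves the near result by the near-specific difference.** With a 35:65 split and an assumed near difference of 0.06 logMAR, this would be 0.15 × 0.06 = 0.009. Section 14.5 lists no covariate-by-distance interaction, so one pooled effect applies. If the assumed effects are 0, 0.03 and 0.06 at the three distances, their simple average gives 0.15 × 0.03 = 0.0045.
- **Covariates will be chosen after the intervals are seen.** The wording does not prevent this, but nothing says that it is planned.

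**Conclusion.** The point holds conditionally. If the target is the mean acuity of the lens in the study population, which is the natural reading of section 2.3, the permitted covariates can make the upper limits too low. One-sided error rises from 2.5% to between 2.8% and 6.4% over assumed R2 of 0.05 to 0.4, and by less if sites differ. With equal-weight class LSMs the main fault is a changed target, not a shorter interval. Its effect may be anti-conservative, conservative or nil, depending on the enrolled split and on which group sees better.

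The size cannot be fixed from the documents, because R2, SD, group splits and site variance are not given. What is firm is that the plan states neither the target mean nor the covariate set nor the LSM weights, although the decisions can depend on them. This is a cheap improvement to make, not evidence that the primary analysis is invalid.

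**What to change.** In section 14.5, base the three superiority decisions on LSMs from the model with distance as fixed effect and site as random effect, without fixed covariates. State that the target is mean acuity in the study population. Report the model with age, gender and add power as a sensitivity analysis only. Name its covariates in advance, say whether add enters in dioptres or as Low/High, and use observed-margin LSMs.

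If the sponsor prefers an adjusted primary analysis, the alternative is to prespecify the covariates, the reference values or weights and the target mean. If that target is the population mean, the standard error must include covariate sampling variation.

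The cost of the main fix is one or two sentences and no new data. Where covariates would have shortened the interval, the primary intervals become wider by 1/sqrt(1-R2) - 1: about 3% at R2 = 0.05, 12% at 0.2 and 29% at 0.4.

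### If acuity varies modestly more at one distance than at another, letting AICC settle on compound symmetry slightly understates that distance's standard error; fixing an unstructured covariance removes this at negligible cost (minor)

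*Combined protocol and SAP*

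**What the plan says.** Section 2.3 sets three separate hypotheses for binocular, high-contrast, high-luminance acuity. At 4 m the "logMAR visual acuity of the test lens will be statistically better than 0.00 logMAR", measured on ETDRS charts. At 64 cm and at 40 cm the threshold is +0.17 logMAR, measured on Guillon-Poling charts.

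Section 14.5 analyses all three in one linear mixed model with distance as a fixed effect. On the residual covariance it says: "Covariance structures considered may include: Homogenous compound symmetry (CS) and Unstructured covariance structure (UN". The choice follows from the fit: "The structure that returns the lowest Akaike Information Criteria Corrected (AICC) will be selected as the structure that best fit the data". Degrees of freedom are by Kenward-Roger.

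The decision is then taken distance by distance. "Comparisons will be carried out using 95% confidence intervals constructed of least-square means (LSM) from the linear mixed models", and "Statistically superiority will be concluded if the upper limits of the confidence intervals are below the thresholds for corresponding distances". Only the upper limit counts, so the nominal one-sided error is 2.5% per distance. Section 14.4 states an overall type I error rate of 5%. Section 14.2 explains that no historical data exist for this lens, and the plan gives no SD for any distance.

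**The concern.** AICC rewards overall fit with few parameters. It does not ask whether each distance's standard error is right, and that is what the decision rule needs. Homogeneous CS replaces three variances by their average. If one distance is more variable than the others and CS is still selected, the interval there is too short and the interval at the least variable distance is too long. The error passes straight into the comparison of the upper limit with the threshold. Nothing in the plan gives a reason to expect equal variances at 4 m, 64 cm and 40 cm, and the charts differ. At stake is a somewhat too easy superiority claim at whichever distance has the most variable acuity.

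**Working it through.** The plan has no SD, power or sample-size calculation, so there is no figure of its own to reproduce. The planned rule was simulated instead.

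**Inputs from the documents:** 80 completers (Section 4.1); 95% limits read one-sided at each distance; CS or UN by lowest AICC (Section 14.5).

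**Assumptions:** SDs around 0.10 logMAR; within-subject correlation 0.5, with 0.2 in some settings; complete data; distance means only, with no site effect or covariates; Satterthwaite df in place of Kenward-Roger under CS, and n − 1 under UN.

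**Step 1. What pooling does if CS is used.** Under CS the variance at every distance is the mean of the three variances. The one-sided error at a distance is approximately 1 − Φ(1.96 × pooled SD / true SD).

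- SDs 0.10/0.10/0.12: pooled variance (0.0100 + 0.0100 + 0.0144)/3 = 0.01147, pooled SD 0.1071. Most variable: 1.96 × 0.1071/0.12 = 1.749, error 4.0%.
- SDs 0.09/0.10/0.11: pooled variance (0.0081 + 0.0100 + 0.0121)/3 = 0.01007, pooled SD 0.1003. Most variable: 1.96 × 0.912 = 1.788, error 3.7%. Least variable: 1.96 × 1.115 = 2.185, error 1.4%.

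**Step 2. How much evidence AICC needs to leave CS.** AICC = −2logL + 2kN*/(N* − k − 1), with N* = 3 × 80 − 3 = 237. The penalty is 4 × 237/234 = 4.05 for CS (k = 2) and 12 × 237/230 = 12.37 for UN (k = 6). CS is kept unless UN improves −2logL by more than 8.31, so modest variance differences are often missed.

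**Step 3. Error of the whole procedure** (n = 80, 100,000 trials per setting). The error columns refer to the most variable distance; correlation is 0.5 unless two values are shown.

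| True SDs | Largest/smallest | CS chosen | Error, averaged over selection | Error when CS is chosen |
|---|---|---|---|---|
| equal | 1.0 | 91% | 2.5% | at nominal |
| 0.10/0.10/0.11 | 1.1 | 81% | 3.0% | not tabulated |
| 0.10/0.10/0.12 | 1.2 | 52% (61% at correlation 0.2) | 3.1% to 3.2% | 4.1% to 4.2% |
| 0.09/0.10/0.11 | 1.22 | 56% (65% at 0.2) | about 3.1% | about 3.7% |
| 0.10/0.10/0.125 | 1.25 | 35% | 3.0% | not tabulated |
| 0.10/0.10/0.13 | 1.3 | 21% | 2.8% | not tabulated |
| 0.085/0.10/0.115 | 1.35 | 22% (34% at 0.2) | 2.8% to 3.0% | about 4.2% to 4.6% |
| 0.08/0.10/0.12 | 1.5 | 4% | 2.6% | not tabulated |
| 0.10/0.10/0.15 | 1.5 | 1% | 2.6% | not tabulated |
| 0.10/0.10/0.20 | 2.0 | about 0% | 2.5% | not applicable |

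The error given CS rises with the SD ratio, but CS is then chosen less and less often; hence the peak in the averaged column. When CS is chosen, the least variable distance is conservative: about 1.4% to 1.5% for SDs 0.09/0.10/0.11 and 1.1% for 0.085/0.10/0.115. UN held 2.4% to 2.6% at every distance in every setting.

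**Step 4. Chance of at least one false claim**, with all three means at their thresholds:

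| True SDs | Correlation | AICC choice | Always UN |
|---|---|---|---|
| 0.09/0.10/0.11 | 0.2 | 7.2% | 7.1% |
| 0.09/0.10/0.11 | 0.5 | 6.4% | 6.3% |
| 0.085/0.10/0.115 | 0.2 | 7.2% | 7.0% |
| 0.085/0.10/0.115 | 0.5 | 6.5% | 6.3% |

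Across all checks the difference was about 0.1 to 0.25 points.

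**Step 5. Price of UN when the variances are equal.** At correlation 0.5 the critical value is 1.990 under UN (79 df) and 1.975 under CS (158 df), a ratio of 1.008. Simulated half-widths at SD 0.10 were 0.0222 under UN and 0.0220 to 0.0221 under CS. At a standardized effect of 0.31, power is 79.1% against 79.6%.

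**The case against.** The strongest reply is that the rule largely protects itself. With equal variances CS is correct, and when variances differ clearly AICC moves to UN (96% to 99% of trials at a ratio of 1.5 and correlation 0.5). Harm is confined to a narrow band, and nothing in the documents shows that this lens falls in it; different charts alone do not establish unequal SDs. That stands, and it is why the point is minor.

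Three stronger readings are tempting but unsupported:

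- A reader might infer that the plan makes the interval at the most variable distance too narrow as a matter of course. It does so only when CS is chosen while the variances differ.
- A reader might take 3.7% to 4.6% as the plan's error rate. Those figures are conditional on CS being chosen. The planned procedure is to select and then test, so its error is the averaged one.
- A reader might blame the covariance choice for exceeding the overall 5% in Section 14.4. In Step 4 the chance of any false claim exceeds 5% under UN as well. That excess comes from testing three hypotheses, a separate question which UN does not settle.

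It is also fair to say that Section 14.5 fixes its criterion in advance and cites a reference for it. The candidate list is open, so a heterogeneous structure is not excluded; the calculation assumes a closed choice between CS and UN. Section 14.2 calls the study a pilot, which lowers the stakes. None of this gives a reason to prefer the selection step, which gains almost nothing at this sample size.

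**Conclusion.** The concern holds in limited form. For SD ratios of about 1.1 to 1.35 with 80 completers, the averaged one-sided error at the most variable distance is about half a point above nominal (2.8% to 3.2% against 2.5%), with the least variable distance conservative. Outside that band the error is at or near nominal.

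The size depends on assumed SDs and correlations and on the reduced model set out above. Random site, the age, gender and add-power covariates, Kenward-Roger df and missing data were not simulated, so the behaviour and convergence of UN in the full planned model remain untested. This is a small improvement to make, not a threat to the trial's conclusions.

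**What to change.** In Section 14.5, replace the AICC selection with a fixed structure, for example: *The residual covariance among the three distances within a subject will be unstructured. If this model does not converge, heterogeneous compound symmetry will be used.* The fallback applies only to non-convergence and should keep a separate variance for each distance.

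This gives each distance its own standard error and also closes the open candidate list. The cost is a sentence or two of text and four more covariance parameters (six instead of two, from 3 × 80 = 240 observations). If the variances are in truth equal, intervals are under 1% wider and about half a point of power is lost. Design, data collection and clinical procedures are unaffected.

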14.6. Secondary Analysis

Not Applicable

14.7. Other Exploratory Analyses

Not Applicable

14.8. Interim Analysis

An interim analysis will not be performed on this study.

14.9. Procedure for Handling Missing Data and Drop-Outs

Missing or spurious values will not be imputed. The count of missing values will be included in the summary tables and listings.

14.10. Procedure for Reporting Deviations from Statistical Plan

The analysis will be conducted according to that specified in above sections. There are no known reasons for which it is planned to deviate from these analysis methods. If for any reason a change is made, the change will be documented in the study report along with a justification for the change.

15. DATA HANDLING AND RECORD KEEPING/ARCHIVING

15.1. Electronic Case Report Form/Data Collection

The data for this study will be captured on electronic case report forms (eCRFs) using an EDC system (Bioclinica). An authorized data originator will enter study data into the eCRFs using the EDC system. Data collected on equipment that is not captured in EDC will be formatted to the specification of the JJVC database manager and sent to JJVC for analysis.

The clinical data will be recorded on dedicated eCRFs specifically designed to match the study procedures for each visit. Only specifically delegated staff can enter data on a CRF. Once completed, the eCRFs will be reviewed for accuracy and completeness and signed by the Investigator. The sponsor or sponsor's representatives will be authorized to gain access to the subject recordation for the purposes of monitoring and auditing the study.

Edit checks, electronic queries, and audit trails are built into the system to ensure accurate and complete data collection. Data will be transmitted from the clinical site to a secure central

Clinical Study Protocol

Johnson & Johnson Vision Care, Inc.

database as forms are completed or updated, ensuring information accuracy, security, and confidentiality. After the final database lock, the Investigator will be provided with Individual Patient Profiles (IPP) including the full audit trail on electronic media in PDF format for all of the study data. The IPP must be retained in the study files as a certified copy of the source data for the study.

The content and structure of the eCRFs are compliant with ISO14155:2020.¹

15.2. Subject Record

At a minimum, subject record should be available for the following:

- subject identification
- eligibility
- study identification
- study discussion
- provision of and date of informed consent
- visit dates
- results of safety and efficacy parameters as required by the protocol
- a record of all adverse events
- follow-up of adverse events
- medical history and concomitant medication
- test article receipt/dispensing/return records
- date of study completion
- reason for early discontinuation of test article or withdrawal from the study, if applicable

The subject record is the eCRF or an external record. The author of an entry in the subject record must be identifiable. The first point of entry is considered to be the source record.

Adverse event notes must be reviewed and initialed by the Investigator.

